8.1.1. Biological samples

Approximately 80 mL of blood will be collected during the entire study period.

Table 7 Biological samples

Sample type	Quantity	Unit	Time point	Subset name*
Blood	At least 25 mL	mL	Days 1, 22, and 43	All participants

* Refer to Section [6.3.4](#) for subset description.

8.1.2. Laboratory assays

All laboratory testing will be performed in a laboratory designated by GSK Biologicals.

Microneutralization and hemagglutination inhibition (HI) assays development, qualification and clinical testing will be outsourced.

Table 8 Laboratory assays

Assay type	System	Component	Challenge	Method	Laboratory*
Humoral Immunity (Antibody determination)	Serum	Vaccine-homologous Influenza A/Hong Kong/125/2017-like Virus		HI	Q ² Solutions
	Serum	Vaccine-homologous Influenza A/Hong Kong/125/2017-like Virus		MN	Q ² Solutions

* Refer to the list of clinical laboratories for details.

HI: hemagglutination inhibition; MN: microneutralization

Please refer to the Section [10.2](#) for a brief description of the assays performed in the study.

The addresses of clinical laboratories used for sample analysis are provided in a separate document accompanying this study protocol.

The clinical laboratories have established a Quality System supported by procedures. The activities of the clinical laboratories are audited regularly for quality assessment by an internal (sponsor-dependent) but laboratory-independent Quality Department. Clinical laboratories contracted by GSK also conform to Good Laboratory Practice guidelines and operate in compliance with regulatory standards.

8.1.3. Immunological read-outs

Table 9 Immunological read-outs

Blood sampling time point		Subset name	No. participants	Component	Components priority rank
Type of contact and timepoint	Sampling time point				
Visit 1 (Day 1)	Pre-Vacc I	HI	840	Vaccine-homologous Influenza A/Hong Kong/125/2017-like Virus	1
Visit 1 (Day 1)	Pre-Vacc I	MN	420	Vaccine-homologous Influenza A/Hong Kong/125/2017-like Virus	2
Visit 2 (Day 22)	Pre-Vacc II	HI	840	Vaccine-homologous Influenza A/Hong Kong/125/2017-like Virus	1
Visit 2 (Day 22)	Pre-Vacc II	MN	420	Vaccine-homologous Influenza A/Hong Kong/125/2017-like Virus	2
Visit 3 (Day 43)	Post-Vacc II	HI	840	Vaccine-homologous Influenza A/Hong Kong/125/2017-like Virus	1
Visit 3 (Day 43)	Post-Vacc II	MN	420	Vaccine-homologous Influenza A/Hong Kong/125/2017-like Virus	2

HI: hemagglutination inhibition; MN: microneutralization; Post-Vacc: post-vaccination; Pre-Vacc: pre-vaccination

8.1.4. Immunological correlates of protection

Although there is no accepted correlate of protection against influenza virus, either seasonal or pandemic, the protective role of antibodies against HA and, to a lesser extent, neuraminidase, is well established and has been demonstrated both in experimentally infected animals and humans [Rimmelzwaan, 2008]

For this reason, the induction of HA-specific antibodies is used as a marker of potential vaccine efficacy and the serum HI assay is used to demonstrate this humoral response. Hemagglutination inhibition antibody titers of 1:40 or greater have been associated with protection from influenza illness in at least 50% of participants in challenge studies [Hannoun, 2004] and correlate with vaccine effectiveness [Beyer, 1989].

8.2. Safety Assessments

The investigator and any designees are responsible for detecting, documenting, and reporting events that meet the definition of an AE or SAE. The investigator and any designees remain responsible for following up AEs that are serious, considered related to the study intervention or the study, or that caused the participant to discontinue the study.

8.2.1. Pre-vaccination procedures

8.2.1.1. Informed consent

The signed informed consent of the participant must be obtained before study participation. Refer to Section 10.1.3 for the requirement on how informed consent will be obtained.

8.2.1.2. Check inclusion and exclusion criteria

All inclusion and exclusion criteria will be checked as described in Sections 5.1 and 5.2 before dosing on Day 1.

8.2.1.3. Collection of demographic data

Demographic data such as age, year of birth, gender, height, weight, race, and ethnicity will be recorded in the participant's eCRF.

8.2.1.4. Medical history

Obtain the participant's medical history by interviewing the participant and/or review of the participant's medical records. Record any pre-existing participant conditions, signs and/or symptoms present prior to the first vaccination in the eCRF.

8.2.1.5. Physical examination

At a minimum, temperature and vital signs (e.g. heart rate and respiratory rate, blood pressure) must be collected. Participants will undergo a physical examination and vital signs are to be taken prior to the first vaccination and will consist of 1 heart rate and 1 blood pressure measurement. Blood pressure and pulse measurements will be assessed by a completely automated device. Manual techniques will be used only if an automated device is not available. Collected information will be recorded in the eCRF.

If the investigator determines that the participant's health on the day of vaccination temporarily precludes vaccination, the visit will be rescheduled.

8.2.1.6. History of adjuvanted vaccine and influenza vaccine

For each of the 2017/2018, 2018/2019, and 2019/2020 influenza seasons, record whether the participant received an adjuvanted vaccine or influenza vaccine and if so, the administration method in the eCRF.

8.2.1.7. Pregnancy test

Female participants of childbearing potential must perform a urine pregnancy test prior to any study vaccine administration. Pregnancy testing must be performed even if the participant is menstruating at the time of the study visit. The study vaccine/product may only be administered if the pregnancy test is negative.

Refer to the Section [10.5.3.1](#) for the information on study continuation for participant who becomes pregnant during the study.

8.2.1.8. Assess pre-vaccination body temperature

The body temperature of the participant must be measured prior to any study vaccine/product administration. The preferred location for recording temperature in this study is oral. If the participant has a temperature $\geq 38.0^{\circ}\text{C}/100.4^{\circ}\text{F}$ by any route on the day of dosing, the dosing visit will be rescheduled within the allowed interval ([Table 2](#)).

8.2.2. Study holding rules and safety monitoring

8.2.2.1. Internal Safety Review Committee

At least 2 iSRC reviews are planned.

The iSRC members are GSK employees and will not be otherwise involved in the conduct of the study and will be independent from GSK's Pandemic Influenza Safety Review Team. The iSRC members will have access to all available data. The iSRC composition, responsibilities and operational details will be outlined in an iSRC charter.

8.2.2.2. Outcome of safety evaluation

During each iSRC review, reactogenicity and safety data for approximately 140 participants (approximately 10 participants per vaccine group and placebo group stratified by age) will be monitored. The first iSRC review will occur when data collected for 7 days post dose (i.e. Day 1 to Day 7, inclusive) are available; the second review will occur based on the available data collected 7 days post dose 2 (i.e. Day 22 to Day 28, inclusive) for the same group of participants. Additional iSRC reviews may be carried out as needed.

If a safety signal is observed, GSK may decide to suspend further vaccinations in all groups or in selected groups. Guidance about how to proceed will be provided should such a decision be made.

8.2.2.3. Study holding rules

The safety holding rules are defined in [Table 10](#). Holding rules 1a-b will be assessed by each investigator on a continuous basis. Meeting any of these holding rules will trigger a hold of vaccination irrespective of number of participants enrolled and/or timing of the event.

The final responsibility to recommend whether the study should be continued in all or in selected groups, modified or stopped permanently, rests with the Sponsor, after having considered all the safety information available. If the study is stopped or modified, a letter indicating the reasons will be sent to the IRB(s)/IEC(s) via the investigator(s), and to Center for Biologics Evaluation and Research (CBER), via GSK.

Of note, no formal holding rules will be applied for other safety data such as non-life-threatening SAEs, missed visits due to vaccine-related AEs, Grade 1 and Grade 2 solicited administration site and systemic events and unsolicited AEs in the 7-day follow-up period and unsolicited AEs collected from Day 8 to Day 22 and Day 29 to Day 43 after vaccination. However, if available, these data will also be reviewed by the iSRC in order to allow an overall assessment of the benefit/risk ratio of vaccination.

Table 10 Study holding rules

Holding Rule	Event	Number of Participants
1a	Death or any life-threatening SAE that can be reasonably attributed to the vaccination	≥ 1
1b	Any non-life-threatening SAE that can be reasonably attributed to the vaccination occurring within 21 days from vaccination	≥ 1

If any investigator becomes aware of a holding rule being met, he/she will suspend vaccination and inform the PPD Medical Monitor immediately (e.g. meeting of holding rules 1a-b). Refer to the [Table 13](#) for contact information.

When a holding rule is identified the following communication flow will occur:

1. The investigator will notify the PPD Medical Monitor by calling the PPD Pharmacovigilance SAE Hotline at [name].
2. The PPD Medical Monitor or delegate will notify the study sites and IRT manager. The IRT manager will block IRT from allowing randomization (or screening, if applicable). Study sites will not randomize or screen participants until notification that the hold is released.
3. The study site will confirm receipt of notification (in writing). Clinical team manager at PPD will collect study site acknowledgement.
4. PPD Medical Monitor will notify GSK Clinical Research and Development Lead.

5. GSK Clinical Research and Development Lead will notify Vaccine Safety Monitoring Board (VSMB) and iSRC.
6. iSRC will review unblinded data and make recommendation to VSMB.
7. VSMB will make final decision whether to continue or stop the study.
8. GSK will notify CBER.

8.3. Adverse Events (AEs), Serious Adverse Events (SAEs) and other events of interest

8.3.1. Time period and frequency for collecting AE, SAE and other safety information

Table 11 Timeframes for collecting and reporting of safety information

Event	Pre- V1*	V1 D1	V1 D7	V2 D22	V2 D28	V3 D43	TC3 M4	TC4 M7	TC5 M10	TC6 M13
Solicited administration site and systemic events										
Unsolicited AEs and MAEs										
SAEs										
Pregnancy										
pIMDs										

* i.e. consent obtained.

AEs: adverse events; D: Day; M: Month; MAEs: medically attended adverse events; pIMDs: potential immune-mediated diseases; Pre-V: pre-vaccination; SAE: serious adverse events; TC: telephone contact; V: vaccination

The investigator or designee will record and immediately report all SAEs to the sponsor or designee via the Expedited AE Reporting Form. This reporting should, under no circumstances, occur later than 24 hours after the investigator becomes aware of an SAE, as indicated in Section 10.3.10. The investigator will submit any updated SAE data to the sponsor within 24 hours of it being available.

A post-study AE/SAE is defined as any event that occurs outside of the AE/SAE reporting periods defined in [Table 11](#). Investigators are not obligated to actively seek AEs or SAEs in former study participants. However, if the investigator learns of any SAE, including a death, at any time after a participant has been discharged from the study, and he/she considers the event to be reasonably related to the study vaccine/product, the investigator will promptly notify the Study Contact for Reporting SAEs mentioned in the [Table 13](#).

8.3.2. Method of detecting AEs and SAEs, pregnancies and other events

Methods of detecting and recording AE/SAE/pIMDs/pregnancies are detailed in the Section [10.3.8](#). The assessment of AE/SAE intensity, causality and outcome are provided in the Section [10.3.9](#).

Open-ended and non-leading verbal questioning of the participants is the preferred method of acquiring information related to an AE/SAE/pIMDs/pregnancy.

8.3.2.1. Clinically significant abnormal laboratory findings

Clinical laboratory measurements are not scheduled to be taken during the study; however, clinical laboratory tests may be performed and the results obtained as part of critical care or follow-up due to the occurrence of medically attended adverse events (MAEs), SAEs, or pIMDs during the study.

The investigator must review the laboratory report, document that he/she did so, and record any clinically relevant changes occurring during the study in the eCRF. Clinically significant abnormal laboratory findings are those which are associated with an underlying disease judged by the investigator to be more severe than expected for the participant's condition.

8.3.3. Regulatory reporting requirements for SAEs, pregnancies, and other events

Once an investigator (or designee) becomes aware that a study participant has experienced an SAE/pIMDs/pregnancy, he/she must report it to PPD Pharmacovigilance using the required documentation, and within the timeframes, mentioned in the [Table 12](#). This is essential for meeting legal obligations and ethical responsibilities for participant safety and the safety of a study intervention under clinical investigation.

For SAEs/pIMDs, the investigator will always provide an assessment of causality at the time of the initial report, as defined in the Section [10.3.9.2](#).

Local regulatory requirements and sponsor policy for the preparation of an investigator safety report for SUSAR must be followed. These reports will be forwarded to investigators as necessary.

The sponsor has a legal responsibility to notify regulatory agencies about the safety of a study intervention under clinical investigation. The sponsor will comply with country-specific regulatory requirements related to safety reporting to the regulatory authority, IRB/IEC, and investigators.

Please refer to Section 10.3.10 for further details regarding the reporting of SAEs/pIMDs/pregnancies.

Table 12 Timeframes for submitting serious adverse event, pregnancy and other events reports to PPD Pharmacovigilance

Type of Event	Initial Reports		Follow-up of Relevant Information on a Previous Report	
	Timeframe	Documents	Timeframe	Documents
SAEs	24 hours*‡	Electronic Expedited Adverse Events Report	24 hours*	Electronic Expedited Adverse Events Report
Pregnancies	24 hours* (Amended 22 February 2022)	Paper pregnancy notification report	24 hours* (Amended 22 February 2022)	Paper pregnancy follow-up report
pIMDs	24 hours** ‡	Electronic Expedited Adverse Events Report	24 hours*	Electronic Expedited Adverse Events Report

* Timeframe allowed after receipt or awareness of the information by the investigator/site staff.

** Timeframe allowed once the investigator determines that the event meets the protocol definition of a pIMDs.

‡ The investigator will be required to confirm review of the SAE/pIMDs causality by ticking the 'reviewed' box in the electronic Expedited Adverse Events Report within 72 hours of submission of the SAE/pIMDs.

8.3.4. Treatment of adverse events

Any medication administered for the treatment of an SAE/pIMD should be recorded in the Expedited Adverse Events Report of the participant's eCRF screen (refer to the Section 10.3.10.1).

8.3.5. Participant card

The investigator (or designee) must provide the participant with a “participant card” containing information about the clinical study. The participant must be instructed to keep the participant card in his/her/their possession at all times throughout the study. In an emergency, this card serves to inform the responsible attending physician that the participant is in a clinical study and that relevant information may be obtained by contacting the investigator.

8.4. Treatment of overdose

For this study, any dose of study intervention greater than 1.9 μg , 3.75 μg , or 7.5 μg given outside of the Study Day 18 to Study Day 25 interval will be considered an overdose.

GSK does not recommend specific treatment for an overdose.

8.5. Pharmacokinetics

Pharmacokinetic parameters are not evaluated in this study.

8.6. Pharmacodynamics

Pharmacodynamic parameters are not evaluated in this study.

8.7. Genetics

Not applicable

8.8. Biomarkers

Not applicable

8.9. Health outcomes

Not applicable

9. STATISTICAL CONSIDERATIONS**9.1. Statistical hypotheses**

The hypothesis test is planned to demonstrate whether vaccination with monovalent influenza A/Hong Kong/125/2017-like (H7N9) virus vaccine containing 1.9 μg , 3.75 μg or 7.5 μg of HA adjuvanted with AS03A or AS03B elicits an HI antibody response to the vaccine-homologous virus that meets or exceeds the CBER immunogenicity criteria 21 days after the second dose of H7N9 vaccine [[CBER](#), 2007].

Each null hypothesis (H_0) is that the lower limit (LL) of the confidence interval (CI) for seroconversion (SCR)/seroprotection (SPR) rate will not meet or exceed the threshold set in the CBER guidelines. Each alternative hypothesis (H_a) is that the LL of the CI for the SCR/SPR meets or exceeds the threshold set in the CBER guidelines. The overall type I error rate is fixed at 5% for each age group, and a Bonferroni adjustment was applied to allow simultaneous multiple comparisons of each antigen/adjuvant group.

9.2. Sample size determination

Approximately 840 participants will be randomized to achieve 798 evaluable participants.

Withdrawals will not be replaced.

9.2.1. Immunogenicity

The primary immunogenicity objective of the study is to evaluate whether vaccination with monovalent influenza A/Hong Kong/125/2017-like (H7N9) virus vaccine containing 1.9 μ g, 3.75 μ g or 7.5 μ g of HA adjuvanted with AS03A or AS03B elicits an HI antibody response to the vaccine-homologous virus that meets or exceeds the US Food and Drug Administration, CBER immunogenicity criteria at the Day 43 visit. [CBER, 2007].*

* The age appropriate CBER criteria will be used and assessed separately:

- CBER immunogenicity criteria for SCR for 18 to 64 years of age will be shown if the LL of the 99.17% CI for SCR meets or exceeds 40%.
- CBER immunogenicity criteria for SPR for 18 to 64 years of age will be shown if the LL of the 99.17% CI for the incidence rate of HI Reciprocal Titers ≥ 40 meets or exceeds 70%.
- CBER immunogenicity criteria for SCR for ≥ 65 years of age will be shown if the LL of the 99.17% CI for SCR meets or exceeds 30%.
- CBER immunogenicity criteria for SPR for ≥ 65 years of age will be shown if the LL of the 99.17% CI for the incidence rate of HI Reciprocal Titers ≥ 40 meets or exceeds 60%.

A total of 840 participants are planned to be enrolled, with 60 participants per antigen/adjuvant/age group. A drop-out/protocol violation rate of not more than 5% yields an approximate sample size of 57 evaluable participants per group, giving 82% overall power to fulfil the CBER (SCR, SPR) immunogenicity criteria in any one of the 12 adjuvanted vaccine treatment groups, assuming that the reference rate for SPR and SCR is 91% and 80% for participants 18 to 64 years of age and 86% and 75% for participants ≥ 65 years of age, respectively.

The 2-sided exact Clopper-Pearson 99.17% CI for SCR or SPR is to allow parallel assessment of the 6 antigen/adjuvant combinations within each age group, addressing multiple comparisons using a Bonferroni adjustment by dividing the 5% Type I error equally 6 ways. Success can be declared for any antigen/adjuvant group within an age range if CBER criteria is met even if any other group does not meet the CBER criteria.

Table 14 presents the power for 1 group to meet the CBER immunogenicity criteria, assuming the enrollment is 60 participants per group and non-evaluable rate is about 5%.

Table 14 Criteria to evaluate primary objective with respect to SCR and SPR for anti-HA, 21 days after the second vaccination

To meet CBER Criteria	Endpoint	Statistical Success Criteria	N evaluable	Reference value	Power*
18-64 years of age	Anti-HA: SCR	LL of 99.17% CI of SCR > 40%	57	80%	99.99%*
	Anti-HA: SPR	LL of 99.17% CI of SPR > 70%	57	91%	86.26%*
≥65 years of age	Anti-HA: SCR	LL of 99.17% CI of SCR > 30%	57	75%	>99.99%*
	Anti-HA: SPR	LL of 99.17% CI of SPR > 60%	57	86%	95.12%*
			Overall power		82%

* Power estimated using PASS 2012, 1-Sided Exact test on the proportions, alpha = 0.415%.

CBER: Center for Biologics Evaluation and Research; CI: confidence interval; HA: hemagglutinin; LL: lower limit; SCR: seroconversion rate; SPR: seroprotection rate.

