4.3 Sample Size

The primary immunogenicity objective of the study is to evaluate whether vaccination with monovalent H7N9 virus vaccine containing 1.9 µg, 3.75 µg or 7.5 µg of HA adjuvanted with AS03_A or AS03_B elicits an HI antibody response to the vaccine-homologous virus that meets or exceeds the [US FDA, CBER](#) immunogenicity criteria at the Day 43 visit.

The age-appropriate CBER criteria will be used and assessed separately:

- CBER immunogenicity criteria for SCR for 18 to 64 years of age will be shown if the lower limit (LL) of the 99.17% CI for SCR meets or exceeds 40%.
- CBER immunogenicity criteria for SPR for 18 to 64 years of age will be shown if the LL of the 99.17% CI for the incidence rate of HI Reciprocal Titers ≥ 40 meets or exceeds 70%.
- CBER immunogenicity criteria for SCR for ≥ 65 years of age will be shown if the LL of the 99.17% CI for seroconversion rate meets or exceeds 30%.
- CBER immunogenicity criteria for SPR for ≥ 65 years of age will be shown if the LL of the 99.17% CI for the incidence rate of HI Reciprocal Titers ≥ 40 meets or exceeds 60%.

The statistical testing sequence is illustrated below. The 6 antigen/adjuvant combinations will be assessed simultaneously for a particular endpoint (SCR or SPR) and age category using Bonferroni Type 1 error adjustment. The order of statistical testing is SCR for 18-64 years of age, SPR for 18-64 years of age, SCR for ≥ 65 years of age, SPR for ≥ 65 years of age. Testing will progress in the sequence only if current test is a success, so that no further adjustment of alpha is needed. Success is reached if at least one antigen/adjuvant combination does fulfill the CBER requirements for SCR and for SPR for at least one age category after all permitted statistical tests are completed.

F1: 1.9 µg HA + AS03B; F2: 1.9 µg HA + AS03A; F3: 3.75 µg HA + AS03B; F4: 3.75 µg HA + AS03A; F5: 7.5 µg HA + AS03B; F6: 7.5 µg HA + AS03A

A total of 840 participants are planned to be enrolled, with 60 participants per antigen/adjvant/age group. A drop-out/protocol violation rate of not more than 5% yields an approximate sample size of 57 evaluable participants per group, giving 82% overall power to fulfil the CBER (SCR, SPR) immunogenicity criteria in any one of the 12 adjuvanted vaccine intervention groups, assuming that the reference rate for SPR and SCR is 91% and 80% for participants 18 to 64 years of age and 86% and 75% for participants ≥ 65 years of age, respectively.

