The 2-sided exact Clopper-Pearson 99.17% CI for SCR or SPR is to allow parallel assessment of the 6 antigen/adjvant combinations addressing multiple comparisons using a Bonferroni adjustment by dividing the 5% Type I error (two-sided tests) equally 6 ways. Success can be declared for any antigen/adjvant group if CBER criteria is met even if any other group does not meet the CBER criteria.

Table 7 presents the power for 1 group to meet the CBER immunogenicity criteria, assuming the enrollment is 60 participants per group and non-evaluable rate is about 5%.

Table 7 Criteria to Evaluate Primary Objective with Respect to SCR and SPR for Anti-HA, 21 Days After the Second Vaccination

To meet CBER Criteria	Endpoint	Stage in testing sequence	Statistical Success Criteria	N evaluable	Reference value	Power*
18-64 years of age	Anti-HA: SCR	1	LL of 99.17% two-sided CI of SCR > 40%	57	80%	99.99%*
	Anti-HA: SPR	2	LL of 99.17% two-sided CI of SPR > 70%	57	91%	86.26%*
≥ 65 years of age	Anti-HA: SCR	3	LL of 99.17% two-sided CI of SCR > 30%	57	75%	>99.99%*
	Anti-HA: SPR	4	LL of 99.17% two-sided CI of SPR > 60%	57	86%	95.12%*
				Overall power		82%

* Power estimated using PASS 2012, 1-Sided Exact test on the proportions, alpha = 0.415%. Overall power is the product of power for the 4 hypotheses within a formulation across the 2 age groups.

CBER: Center for Biologics Evaluation and Research; CI: confidence interval; HA: hemagglutinin; LL: lower limit; SCR: seroconversion rate; SPR: seroprotection rate.

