Since the primary immunogenicity endpoints for the study will be complete by the Day 43 visit (collection past Day 43 includes only assessments for unsolicited AEs leading to study withdrawal, SAEs and pIMDs), no statistical consideration for multiplicity will be given to account for changes in the results reported at the interim analysis compared to the final analysis. For the primary immunogenicity analysis, which will be reported at Day 43 the overall type I error rate is fixed at 5% (two-sided intervals) and a Bonferroni adjustment will be applied to allow simultaneous multiple comparisons of each antigen/adjuvant group. No further adjustment is needed since sequential testing will be used for each antigen/adjuvant group related to the two endpoints and to the two age categories. For the secondary immunogenicity and primary safety analyses no adjustment for multiple comparisons will be made in each antigen/adjuvant group as the CIs are provided for descriptive purposes only. No adjustment is applied for the Placebo group.

11 Changes to the Protocol Planned Analysis

The duration of solicited events will also be summarized by study group, age group and vaccination.

12 References

Center for Biologics Evaluation and Research (CBER). Guidance for Industry. Clinical data needed to support the licensure of pandemic influenza vaccines. May 2007. <https://www.fda.gov/regulatory-information/search-fda-guidance-documents/clinical-data-needed-support-licensure-pandemic-influenza-vaccines>.

Food and Agriculture Organization of the United Nations (FAO). Agriculture and Consumer Protection Department. Animal Production and Health. H7N9 situation update. Avian Influenza A (H7N9) 4 September 2019. http://www.fao.org/ag/againfo/programmes/en/empres/h7n9/situation_update.htm. Accessed 2 October 2019.

World Health Organization (WHO). Avian Influenza Weekly Update Number 694. 20 September 2019. https://www.who.int/docs/default-source/wpro---documents/emergency/surveillance/avian-influenza/ai-20190920.pdf?sfvrsn=30d65594_36. Accessed: 2 October 2019

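### The 82% overall power is attached to any one of 12 groups, but it is the power for one given formulation to meet SCR and SPR in both age groups

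*Protocol*

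**What the plan says.** Protocol 9.2.1 sets enrolment at 840, "with 60 participants per antigen/adjuvant/age group", and adds: "A drop-out/protocol violation rate of not more than 5% yields an approximate sample size of 57 evaluable participants per group". It then describes the design as "giving 82% overall power to fulfil the CBER (SCR, SPR) immunogenicity criteria in any one of the 12 adjuvanted vaccine treatment groups". The assumed rates are SPR 91% and SCR 80% at 18-64 years, and SPR 86% and SCR 75% at 65 and over.

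Protocol Table 14 is introduced as the power for a single group. It lists four powers (99.99%, 86.26%, >99.99% and 95.12%), two for each age group, and ends with an overall power of 82%. Its footnote covers only software, test and alpha: "Power estimated using PASS 2012, 1-Sided Exact test on the proportions, alpha = 0.415" (per cent). It does not define overall power.

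SAP 4.3 repeats the sentence, with the 82% holding "in any one of the 12 adjuvanted vaccine intervention groups", and introduces Table 7 with the same single-group lead-in. The Table 7 footnote then gives a definition: "Overall power is the product of power for the 4 hypotheses within a formulation across the 2 age groups".

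The documents also differ on testing. Protocol 9.2.1 assesses the age groups separately and lets success be declared for any formulation within an age range. SAP 4.3 orders the tests as SCR then SPR at 18-64, followed by SCR then SPR at 65 and over, each step depending on success at the one before. SAP 10.4 says that "sequential testing will be used for each antigen/adjuvant group related to the two endpoints and to the two age categories".

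**The concern.** A count of 12 is possible only if a group is one formulation in one age group, because there are six formulations. The sentence thus describes a success that takes place within a single age group. The 82%, however, sits under four rows drawn from both age groups, and the SAP footnote says that it multiplies across them. That event covers two of the 12 groups.

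This is the stated power for the primary immunogenicity objective. A reader who has only the protocol finds the figure tied to the wrong event in the text, tied to a single group in the table lead-in, and defined nowhere. A reader of the SAP finds the text and the table footnote describing different events under one number.

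**Working it through.** **Inputs.** Evaluable n = 60 × 0.95 = 57 per group. One-sided alpha = (100 − 99.17)/2 = 0.415%. Thresholds and assumed rates are those of protocol 9.2.1 and Table 14. Groups: 6 formulations × 2 age groups = 12 adjuvanted groups. With two placebo age groups, 14 × 60 = 840, which matches the planned enrolment.

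**Step 1: reproduce the four powers.** For threshold p0, the critical count r is the smallest count with P(X ≥ r | 57, p0) ≤ 0.00415. This is the same as requiring the exact 99.17% lower limit to reach p0. Power is P(X ≥ r | 57, p1), where p1 is the assumed rate.

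| Criterion | p0 | p1 | r | Power | Table 14 |
|---|---|---|---|---|---|
| SCR, 18-64 | 40% | 80% | 34 | 0.99988 | 99.99% |
| SPR, 18-64 | 70% | 91% | 50 | 0.86259 | 86.26% |
| SCR, ≥65 | 30% | 75% | 28 | 0.99999 | >99.99% |
| SPR, ≥65 | 60% | 86% | 45 | 0.95120 | 95.12% |

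All four match. Using the unrounded alpha of 0.05/12 gives the same counts.

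**Step 2: reproduce the 82%.** 0.99988 × 0.86259 × 0.99999 × 0.95120 = 0.8204. The two SPR rows alone, one from each age group, give 0.8626 × 0.9512 = 0.8205. The drop to 82% therefore comes from multiplying across age groups.

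**Step 3: power for one given group, with age groups assessed separately as in the protocol.** SCR and SPR come from the same participants, so the product is only an approximation. For any dependence, the joint power lies between P1 + P2 − 1 and min(P1, P2).

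- 18-64: from 0.99988 + 0.86259 − 1 = 0.86247 to 0.86259, about 86%.
- ≥65: 0.95120 at both ends to four decimals, about 95%.

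Differences from the stated figure: 0.8625 − 0.8204 = 0.042, and 0.9512 − 0.8204 = 0.131.

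**Step 4: power for one given group under the SAP sequence, if it runs within each formulation.** An 18-64 group needs the first two steps, which again gives about 86%. A ≥65 group succeeds only if all four steps pass, which gives 0.8204, about 82%.

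**Step 5: other readings of the sentence.** These assume that every group has the reference rates and that the groups are independent.

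- At least one of the 12 groups: 1 − (1 − 0.8625)^6 × (1 − 0.9512)^6 = 1 − 9 × 10⁻¹⁴, practically 100%.
- All 12 groups: 0.8204^6 = 0.305.

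With separate assessment, the only one of these events that has 82% power is one given formulation meeting SCR and SPR in both age groups.

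**The case against.** The best defence concerns the SAP. If its sequence runs within each formulation, as SAP 10.4 reads, a given ≥65 group succeeds only when all four tests pass. Its power is then the 82% that the SAP text states. This stands. In that case the SAP sentence is exact for the six ≥65 groups and about 4 points low for the six 18-64 groups. A reader might infer that both documents understate single-group power by up to 13 points. The 13-point gap needs ungated testing, which is what the protocol describes, and it does not carry over to the SAP on this reading.

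It can also be said that the construction is visible: the overall line sits under four rows from two age groups, and the SAP footnote spells it out. That helps a careful reader of the SAP. It does not supply the definition missing from the protocol, nor does it align the SAP sentence with its footnote. The documents use the word group both for a formulation of 120 and for an age group of 60 within it. That may explain the slip, but a count of 12 fits only the second use.

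Finally, power is a planning statement and does not enter the analysis, and Amendment 2 was written with the study under way. That is a fair argument for treating the point as minor.

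**Conclusion.** The point holds as an inconsistency in definition. The 82% is correctly calculated as the power for one given formulation to meet SCR and SPR in both age groups, and both documents attach it to a different event.

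In the protocol, the text understates the power of one given group by about 4 points (18-64) and 13 points (≥65). In the SAP with sequencing per formulation, only the 18-64 figure is off, by about 4 points. Read as at least one of the 12 groups, the true figure would be near 100% if all groups had the reference rates and were independent.

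These figures rest on 57 evaluable participants per group and the plan's assumed rates. Dependence between SCR and SPR is immaterial, because SCR power is close to 100%.

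A reader might infer an arithmetic error, or that the trial is too small for its primary objective. The documents support neither: all four powers and their product reproduce, and on the plan's assumptions none of the single-group figures is below the stated 82%. Severity is minor.

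**What to change.** 1. In protocol 9.2.1 and SAP 4.3, replace the phrase about any one of the 12 groups with: *for one given formulation to meet SCR and SPR in both age groups*.
2. Copy the overall-power sentence from the SAP Table 7 footnote into the footnote of protocol Table 14.
3. In both documents, change the table lead-in so that it says the rows are per age group and the overall line is per formulation.
4. State the single-group powers: about 86% (18-64) and about 95% (≥65, without gating). In the SAP, add that the power to succeed on the ≥65 criteria is about 82% if the sequence runs within each formulation.

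The cost is one phrase and one lead-in in each document, one copied footnote sentence and a short statement of the single-group powers. No test, threshold or participant number changes.
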